**Required**  
**Show if:** (IASTW.TEXT > 0)

Scale Summary		
Code	Label	Show-If
1		
99	Prefer not to answer	

32. With how many of these **transgender women** did you have **insertive anal sex** without a condom?

- # of transgender women
- Prefer not to answer

Page Break

---

**Question:** IVASTM  
**Required**  
**Show if:** (IVAS ≠ 99:[Prefer not to answer]) and (IVAS.TEXT > 0)

Scale Summary		
Code	Label	Show-If
1		
99	Prefer not to answer	

-  33. How many of these people were **transgender men**? (By transgender men, we mean persons who are considered female at birth and now identify primarily as male.)
- # of transgender men
  - Prefer not to answer

**Question:** IASTM  
**Required**  
**Show if:** (AS ≠ 99:[Prefer not to answer]) and (AS.TEXT > 0) and (IVASTM ≠ 99:[Prefer not to answer]) and (IVASTM ≠ 99:[Prefer not to answer]) and (IVASTM.TEXT > 0)

Scale Summary		
Code	Label	Show-If
1		
99	Prefer not to answer	

-  34. Of these **transgender men**, how many did you have **insertive anal sex** with (with or without a condom)?
- # of transgender men
  - Prefer not to answer

Auto Page Break

---

**Question:** IASTMNC  
**Required**  
**Show if:** (IASTM.TEXT > 0)

Scale Summary		
Code	Label	Show-If
1		
99	Prefer not to answer	

35. With how many of these **transgender men** did you have **insertive anal sex** without a condom?

- # of transgender men
- Prefer not to answer

Page Break

---

The next set of questions ask about your main partner. By main partner, we mean someone who you lived with or saw a lot, or to whom you felt a special emotional commitment, and with whom you had vaginal or anal sex.

Page Break

---

**Question:** MSP

**Required**

**Show if:** (VAS.TEXT >= 1)

Scale Summary		
Code	Label	Show-If
1	Yes	
2	No	
99	Prefer not to answer	

36. Of the persons who you had **vaginal or anal sex** with, is/are any of them your main sexual partner(s)?

- Yes
- No
- Prefer not to answer

Page Break

---

**Collection:** MAIN\_PARTNERS  
**Contains:** MSPCH, MSPNUM, MSPC, MSPID, MSPO, MSPEX, MSPHIV, MSPDR, MSPSTD, MSPWORRIED, OSP  
**Show if:** (MSP = 1:[Yes])

**Question:** MSPCH  
**Required**  
**Show if:** (MSP = 1:[Yes])

Scale Summary		
Code	Label	Show-If
1	Yes	
2	No	
99	Prefer not to answer	

37. Have you changed your main sex partner in the last months?

- Yes
- No
- Prefer not to answer

Auto Page Break

---

**Question:** MSPNUM  
**Required**  
**Show if:** (MSPCH = 1:[Yes])

Scale Summary		
Code	Label	Show-If
1		
99	Prefer not to answer	

38. How many main sex partners have you had in the last months?

- # of main sex partners
- Prefer not to answer

Page Break

---

**Question:** MSPC  
**Required**  
**Show if:** (MSP = 1:[Yes])

Scale Summary		
Code	Label	Show-If
1	Never	
2	Sometimes	
3	Always	
99	Prefer not to answer	

39. How often did you use condoms when you had vaginal or anal sex with your main partner(s) in the last months?

- Never
- Sometimes
- Always
- Prefer not to answer

Page Break

---

**Question:** MSPID  
**Required**  
**Show if:** (MSP = 1:[Yes])

Scale Summary		
Code	Label	Show-If
1	Yes	
2	No	
3	Don't know	
99	Prefer not to answer	

-  40. Do any of your main partner(s) inject drugs to get high?
- Yes
  - No
  - Don't know
  - Prefer not to answer

**Question:** MSPO  
**Required**  
**Show if:** (MSP = 1:[Yes])

Scale Summary		
Code	Label	Show-If
1	Yes	
2	No	
3	Don't know	
99	Prefer not to answer	

-  41. Have any of your main partner(s) had sex with someone else besides you during the same time period?
- Yes
  - No
  - Don't know
  - Prefer not to answer

Auto Page Break

---

**Question:** MSPEX  
**Required**  
**Show if:** (MSPO = 1:[Yes])

Scale Summary		
Code	Label	Show-If
1	Yes	
2	No	
3	Don't know	
99	Prefer not to answer	

 42. Did any of your main partner(s) have vaginal or anal sex with another person in exchange for money, drugs, goods, or services?

- Yes
- No
- Don't know
- Prefer not to answer

Page Break

---

**Question:** MSPHIV  
**Required**  
**Show if:** (MSP = 1:[Yes])

Scale Summary		
Code	Label	Show-If
1	Yes	
2	No	
3	Don't know	
99	Prefer not to answer	

-  43. Are any of your main partner(s) HIV-infected?
- Yes
  - No
  - Don't know
  - Prefer not to answer

**Question:** MSPDR  
**Required**  
**Show if:** (MSP = 1:[Yes])

Scale Summary		
Code	Label	Show-If
1	Yes	
2	No	
3	Don't know	
99	Prefer not to answer	

-  44. Were any of your main partner(s) ever drunk or high on drugs while you were having sex with them?
- Yes
  - No
  - Don't know
  - Prefer not to answer

**Question:** MSPSTD  
**Required**  
**Show if:** (MSP = 1:[Yes])

Scale Summary		
Code	Label	Show-If
1	Yes	
2	No	
3	Don't know	
99	Prefer not to answer	

-  45. Have any of your main partner(s) been diagnosed with or treated for a sexually transmitted infection the last months?
- Yes
  - No
  - Don't know
  - Prefer not to answer

Page Break

---

**Question:** MSPWORRIED  
**Required**  
**Show if:** (MSPHIV = 2:[No]) or (MSPHIV = 3:[Don't know])

Scale Summary		
Code	Label	Show-If
1	Very worried	
2	Somewhat worried	
3	Not at all worried	
99	Prefer not to answer	

46. How worried are you that your main partner(s) may become infected with HIV in **the next year?**

- Very worried
- Somewhat worried
- Not at all worried
- Prefer not to answer

Page Break

---

**Question:** OSP  
**Required**  
**Show if:** (MSP = 1:[Yes])

Scale Summary		
Code	Label	Show-If
1	Yes	
2	No	
99	Prefer not to answer	

 47. Are there any other people, not including your main partner(s), that you recently had sex with?

- Yes
- No
- Prefer not to answer

Page Break

---

**Collection:** OTHER\_PARTNERS  
**Contains:** OSPID, OSPSO, OSPEX, OSPHIV, OSPHIVNC, OSPDR, OSPSTD, OSPWORRIED  
**Show if:** (OSP = 1:[Yes])

The next set of questions ask you about the other people you have had sex with recently.

**Question:** OSPID  

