large portion of missing responses or sparse response levels will be excluded upfront from the input covariate data set, and for a given  $\widehat{\psi}_z(W)$ , only a subset of the 88 behavioral survey variables and the aforementioned demographic variables will be included in  $W$ . Then, the missForest method will be used to multiply impute missing covariate values in  $W$ . Next, to accommodate a high-dimensional  $W$ , dimension-reducing screening methods will be used for “classical” algorithms. Modified versions of screening methods in SuperLearner’s R functions `screen.glmnet` and `screen.randomforest` for the time-to-event outcome will be used as two screening algorithms combined with each prediction algorithm. More specifically, a Cox model with lasso penalty will be used in `screen.glmnet`, and a survival forest (R function `rsfc`) will be used in `screen.randomforest`. In `screen.randomforest`, the top 20 variables with the greatest variable importance index will be screened in. Lastly, the estimators will be trained using the screened-in covariates, the prediction accuracy will be evaluated, and the best-performing estimators will be used for predicting HIV-1 risk in each treatment stratum.

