**Table 3. Baseline Risk Behaviors by Treatment Assignment**

	Total	A	B	C
Total Enrolled	xxx (100.0%)	xxx (100.0%)	xxx (100.0%)	xxx (100.0%)
Number Sex Partners in the Last Month				
0	xxx (xx.x%)	xxx (xx.x%)	xxx (xx.x%)	xxx (xx.x%)
1	xxx (xx.x%)	xxx (xx.x%)	xxx (xx.x%)	xxx (xx.x%)
2	xxx (xx.x%)	xxx (xx.x%)	xxx (xx.x%)	xxx (xx.x%)
3-4	xxx (xx.x%)	xxx (xx.x%)	xxx (xx.x%)	xxx (xx.x%)
>=5	xxx (xx.x%)	xxx (xx.x%)	xxx (xx.x%)	xxx (xx.x%)
Median	xxx	xxx	xxx	xxx
Min, Max	xxx, xxx	xxx, xxx	xxx, xxx	xxx, xxx
Had an HIV+ Partner				
Yes	xxx (xx.x%)	xxx (xx.x%)	xxx (xx.x%)	xxx (xx.x%)
Unprotected Receptive Vaginal Sex with a Partner				
Yes	xxx (xx.x%)	xxx (xx.x%)	xxx (xx.x%)	xxx (xx.x%)
Unprotected Insertive Vaginal Sex with a Partner				
Yes	xxx (xx.x%)	xxx (xx.x%)	xxx (xx.x%)	xxx (xx.x%)
Unprotected Insertive Anal Sex with a Partner				
Yes	xxx (xx.x%)	xxx (xx.x%)	xxx (xx.x%)	xxx (xx.x%)
Unprotected Receptive Anal Sex with a Partner				
Yes	xxx (xx.x%)	xxx (xx.x%)	xxx (xx.x%)	xxx (xx.x%)
Exchange of Sex for Money/Gifts				
Yes	xxx (xx.x%)	xxx (xx.x%)	xxx (xx.x%)	xxx (xx.x%)

**HVTNxxx/HPTNxxx:  
 Closed DSMB Report for DSMB meeting on [Date].  
 Data Cutoff date:[Date].**

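### Survey branching leaves partner-risk items unasked for participants with no main partner, and SAP Section 8.6 treats those blanks as ordinary missing data

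*SAP*

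**What the plan says.** **Branching (SAP Appendix B).** Question 36 (MSP) goes to anyone reporting at least one partner and asks whether any of those partners is a main partner. The answers are Yes, No, or prefer not to answer. The collection MAIN_PARTNERS is shown only if MSP = Yes and contains "MSPCH, MSPNUM, MSPC, MSPID, MSPO, MSPEX, MSPHIV, MSPDR, MSPSTD, MSPWORRIED, OSP". Question 47 (OSP), the last item, asks "Are there any other people, not including your main partner(s), that you recently had sex with" and repeats the condition MSP = Yes. The collection OTHER_PARTNERS contains "OSPID, OSPSO, OSPEX, OSPHIV, OSPHIVNC, OSPDR, OSPSTD, OSPWORRIED" and is shown only if OSP = Yes.

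**HIV-infected-partner items.** There are three. MSPHIV ("Are any of your main partner(s) HIV-infected") needs MSP = Yes. OSPHIV needs OSP = Yes. OSPHIVNC, on condomless sex with an HIV-infected partner, needs OSPHIV = Yes.

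**Appendix C.** The abbreviated survey, for sites of the companion trial outside South Africa, has the same branching at questions 8, 19 and 20 to 27.

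**Use.** SAP Section 8.6 draws candidate covariates for the baseline risk score from these surveys. It first removes variables with much missingness or thinly populated answer categories, with no threshold given. Then "the missForest method will be used to multiply impute missing covariate values". SAP Section 8.2 offers that score as an adjustment covariate in a supportive TMLE that may be run. Appendix A, Table 3 has a row "Had an HIV+ Partner" with only a Yes line; the only count shown above it is the total enrolled.

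**The concern.** OSP is the only route to the questions about partners other than a main partner, yet it is closed to people who have no main partner. They are the people for whom those questions are the only source of partner information. The lost items cover partners' injecting, concurrency, exchange sex, HIV status, intoxication and recent STI, and condomless sex with an HIV-infected partner.

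Such participants belong to the target population. Protocol Section 5.1 can be met by anal intercourse with two or more partners. It excludes volunteers in a mutually monogamous relationship of more than a year with a seronegative partner, and it nowhere requires a main partner.

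Two things are at stake: the quality of the baseline risk score, and whether a reader of Table 3 can tell a participant who said No from one who was never asked.

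**Working it through.** The plan states no figure to reproduce. The check is a trace of the survey logic, then of the missing-data rule, then an illustration of size.

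**1. Which HIV-infected-partner items can be reached (at least one partner reported)?**

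| MSP | Answer OSP gets, or would get if asked | Reached as written | Reached if OSP went to everyone with a partner |
|---|---|---|---|
| Yes | Yes | MSPHIV, OSPHIV, OSPHIVNC | the same |
| Yes | No | MSPHIV | MSPHIV |
| No or declined | Yes | none | OSPHIV, OSPHIVNC |
| No or declined | No | none | none |

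OSPHIVNC still needs OSPHIV = Yes. The third row is the defect.

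**2. How many questions are lost?** MAIN_PARTNERS has 11 items (questions 37 to 47) and OTHER_PARTNERS has 8 (questions 48 to 55): 11 + 8 = 19 of 88. In Appendix C, questions 9 to 27 are again 19, of 60. Ten of the 19 concern a main partner and do not apply to someone without one. One (OSP) is the gate. The other eight do apply.

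**3. What does Section 8.6 do with the blanks?** It has two outcomes.
- If missingness counts as large, the variable is dropped for everyone, including those who answered.
- Otherwise missForest fills it. OSPHIV is observed only where MSP = Yes and OSP = Yes, so a casual-only participant's value is predicted entirely from people who have both a main partner and another partner. Using MSP as a predictor does not help, because no OSPHIV answer exists at MSP = No from which to learn a difference. By the same rule MSPHIV would be filled for a main partner who does not exist.

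Nothing in Section 8.6 marks a value as not asked, and no sensitivity analysis covers it.

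**4. Size for Table 3 (conditional).** Assume that the row is derived from MSPHIV and OSPHIV and divided by all enrolled. Among participants with a partner, let c be the share with MSP = No or declined, p the true proportion with an HIV-infected partner among those with a main partner, and r the ratio of that proportion in the casual-only group to p. Then

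- shown = p(1 − c)
- true = p(1 − c) + c·r·p
- relative understatement = c·r / (1 − c + c·r)

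With r = 1 the understatement equals c. For p = 20% the row shows 18% at c = 10%, 15% at c = 25% and 10% at c = 50%. Letting r run from 0.5 to 1.5:
- c = 10%, r = 0.5: 0.05 / 0.95 = 5%
- c = 50%, r = 1.5: 0.75 / 1.25 = 60%

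The documents give none of c, p and r, so this shows only how the size depends on them. Participants with no partner add nothing to either numerator and leave the ratio unchanged.

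**The case against.** The strongest reply is that little of consequence depends on these items, and much of it stands.

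- **A reader might infer that the derived covariates are wrong.** The documents do not support that. The items are missing by design, then dropped or imputed. Dropping them costs predictive accuracy but adds no false values, and the final estimator is chosen by cross-validated AUC. Partner counts, condom use, condomless anal sex by partner gender, alcohol and drug use, exchange sex and perceived risk do not depend on MSP. A casual-only participant with condomless partners is still recorded as such; what is lost is what those partners were like.
- **A reader might infer that exposure reported to the DSMB is understated by a known amount.** Table 3 is a mock shell and the derivation of the row is not given. Protocol Section 7.2 also requires a risk assessment before enrollment, so another source is possible. No monitoring guideline in SAP Sections 9.1 to 9.4 uses the row. The survey's notion of a main partner is broad (living together, frequent contact or an emotional bond each suffice), which may keep the affected group small.
- **A reader might infer that prevention efficacy is biased.** The primary analysis in SAP Section 8.1 uses no survey covariates. The TMLE is supportive and optional, and missingness at baseline should not depend on the randomized arm.
- **A reader might infer that change-in-risk analyses are spoiled.** The questionnaire is repeated at infusion visits, but Section 8.6 specifies only a baseline score. No planned longitudinal analysis of these items exists to be harmed.

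The reply does not answer the central point. Section 8.6 states a rule for missing values, and applied as written it treats questions never put to a participant as answers that the participant failed to give.

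**Conclusion.** The point holds in limited form. As printed, participants who report partners but answer No or decline at MSP are never asked any HIV-infected-partner item, nor the other OTHER_PARTNERS items that apply to them. Section 8.6 then either discards those variables or imputes them from people who have a main partner. This follows from the show-if conditions and the imputation rule alone.

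The effect is a weaker baseline risk score, which feeds exploratory objective 3 and the optional supportive TMLE. An undercount in Table 3 follows only if its row comes from MSPHIV and OSPHIV over all enrolled. Its size cannot be stated, because the share without a main partner is not given. The primary efficacy analysis is not affected.

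**What to change.** **For data already collected.** In SAP Section 8.6, state that items skipped by branching are coded as a separate not-asked level (or that an MSP indicator enters with them), and that they are not imputed as ordinary non-response. In Appendix A, Table 3, report how many participants were asked about HIV-infected partners, add a separate not-asked row, and state how the row is derived. This takes a few sentences and changes no primary analysis.

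**For any future administration.** In Appendices B and C, show OTHER_PARTNERS when OSP = Yes, or when MSP is not Yes and at least one partner is reported. Five items (OSPID, OSPSO, OSPHIV, OSPDR, OSPSTD) repeat OSP = Yes in their own conditions and must be changed to match. The cost is a few extra questions for those participants.

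The survey edit cannot recover enrollment answers. SAP Section 1 has enrollment finished by September 30, 2018 at the latest, so the baseline covariates can be improved only through the coding.

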**Required**  
**Show if:** (OSP = 1:[Yes])

Scale Summary		
Code	Label	Show-If
1	Yes	
2	No	
3	Don't know	
99	Prefer not to answer	

-  48. During the last months, did you have vaginal or anal sex with someone who injected drugs to get high?
- Yes
  - No
  - Don't know
  - Prefer not to answer

**Question:** OSPSO  
**Required**  
**Show if:** (OSP = 1:[Yes])

Scale Summary		
Code	Label	Show-If
1	Yes	
2	No	
3	Don't know	
99	Prefer not to answer	

-  49. During the last months, did you have vaginal or anal sex with someone who was having sex with someone else besides you during the same time period?
- Yes
  - No
  - Don't know
  - Prefer not to answer

Auto Page Break

---

**Question:** OSPEX  
**Required**  
**Show if:** (OSPSO = 1:[Yes])

Scale Summary		
Code	Label	Show-If
1	Yes	
2	No	
3	Don't know	
99	Prefer not to answer	

50. Did any of these persons have vaginal or anal sex with another person in exchange for money, drugs, goods, or services?

- Yes
- No
- Don't know
- Prefer not to answer

Page Break

---

**Question:** OSPHIV**Required****Show if:** (OSP = 1:[Yes])

Scale Summary		
Code	Label	Show-If
1	Yes	
2	No	
3	Don't know	
99	Prefer not to answer	

51. During the last months, did you have vaginal or anal sex with someone who was HIV-infected?

- Yes
- No
- Don't know
- Prefer not to answer

Auto Page Break

---

**Question:** OSPHIVNC  
**Required**  
**Show if:** (OSPHIV = 1:[Yes])

Scale Summary		
Code	Label	Show-If
1	Yes	
2	No	
3	Don't know	
99	Prefer not to answer	

-  52. Did you have **vaginal or anal sex** without a condom with any HIV-infected persons?
- Yes
  - No
  - Don't know
  - Prefer not to answer

Page Break

---

**Question:** OSPDR  
**Required**  
**Show if:** (OSP = 1:[Yes])

Scale Summary		
Code	Label	Show-If
1	Yes	
2	No	
3	Don't know	
99	Prefer not to answer	

53. During the last months, did you have vaginal or anal sex with someone who was drunk or high on drugs while you were having sex with them?

- Yes
- No
- Don't know
- Prefer not to answer

Page Break

---

**Question:** OSPSTD  
**Required**  
**Show if:** (OSP = 1:[Yes])

Scale Summary		
Code	Label	Show-If
1	Yes	
2	No	
3	Don't know	
99	Prefer not to answer	

-  54. During the last months, did you have vaginal or anal sex with someone who has recently been diagnosed with, or treated for one or more sexually transmitted infections?
- Yes
  - No
  - Don't know
  - Prefer not to answer

**Question:** OSPWORRIED  
**Required**  
**Show if:** (OSPHIV = 2:[No]) or (OSPHIV = 3:[Don't know])

Scale Summary		
Code	Label	Show-If
1	Very worried	
2	Somewhat worried	
3	Not at all worried	
99	Prefer not to answer	

-  55. How worried are you that one or more of your sex partners may become infected with HIV in **the next year**?
- Very worried
  - Somewhat worried
  - Not at all worried
  - Prefer not to answer

Page Break

---

**Collection:** PPT\_RISK\_BEHAVIOR

**Contains:** ALCOH, ALCOHNUM, ALCOHB, VASDRUNK, IDUSE, IDNEEDLESHARE, MDKS, MS2HR, CRCO, CRCOS2HR, PRCO, PRCOS2HR, AMPMETH, AMPMETS2HR, METMAN, METMANS2HR, HERMED, HERMEDS2HR, MDMA, MDMAS2HR, WHO, WHOS2HR, POP, POPS2HR, OTHDRUG, OTHDRUG\_FREQ, OTHDRUGS2HR, CIGVAPE, VASEX, HIVINFYR

The next set of questions ask about some other behaviors.

**Question:** ALCOH

**Required**

Scale Summary		
Code	Label	Show-If
1	Never	
2	Monthly or less	
3	2-4 times a month	
4	2-3 times a week	
5	4 or more times a week	
99	Prefer not to answer	

56. During the last months, how often did you have a drink containing alcohol?

- Never
- Monthly or less
- 2-4 times a month
- 2-3 times a week
- 4 or more times a week
- Prefer not to answer

Auto Page Break

---

**Question:** ALCOHNUM

**Required**

**Show if:** (ALCOH ≠ 1:[Never]) and (ALCOH ≠ 99:[Prefer not to answer])

Scale Summary		
Code	Label	Show-If
1	1 or 2	
2	3 or 4	
3	5 or 6	
4	7 to 9	
5	10 or more	
99	Prefer not to answer	

57. During the last months, on a typical day when you were drinking, how many standard drinks containing alcohol did you have?

- 1 or 2
- 3 or 4
- 5 or 6
- 7 to 9
- 10 or more
- Prefer not to answer

**Question:** ALCOHB

**Required**

**Show if:** (ALCOH ≠ 1:[Never]) and (ALCOH ≠ 99:[Prefer not to answer])

Scale Summary		
Code	Label	Show-If
1	Never	
2	Less than monthly	
3	Monthly	
4	Weekly	
5	Daily or almost daily	
99	Prefer not to answer	

58. During the last months, how often did you have 6 or more drinks on one occasion?

- Never
- Less than monthly
- Monthly
- Weekly
- Daily or almost daily
- Prefer not to answer

**Question:** VASDRUNK

**Required**

**Show if:** (VAS ≠ 99:[Prefer not to answer]) and (VAS.TEXT ≠ 0) and (ALCOH ≠ 99:[Prefer not to answer]) and (ALCOH ≠ 1:[Never])

Scale Summary		
Code	Label	Show-If
1	Yes	
2	No	
99	Prefer not to answer	

59. During the last months, did you have vaginal or anal sex while you were drunk?

- Yes
- No
- Prefer not to answer

Page Break

---

**Question: IDUSE**  
**Required**

Scale Summary		
Code	Label	Show-If
1	Yes	
2	No	
99	Prefer not to answer	

60. During the last months, did you inject any drugs to get high?

- Yes
- No
- Prefer not to answer

Auto Page Break

---

**Question:** IDNEEDLESHARE  
**Required**  
**Show if:** (IDUSE = 1:[Yes])

Scale Summary		
Code	Label	Show-If
1	Yes	
2	No	
99	Prefer not to answer	

61. Did you share a needle with others?

- Yes
- No
- Prefer not to answer

Page Break

---

**Question: MDKS  
Required**

Scale Summary		
Code	Label	Show-If
1	Never	
2	Once per week or less	
3	2-3 times a week	
4	4-6 times a week	
5	Every day	
99	Prefer not to answer	

62. During the last months, how often did you use Marijuana, dagga, K2, spice?

- Never
- Once per week or less
- 2-3 times a week
- 4-6 times a week
- Every day
- Prefer not to answer

Page Break

---

**Question:** MS2HR  
**Required**  
**Show if:** (VAS.TEXT > 0) and (MDKS ≠ 1:[Never]) and (MDKS ≠ 99:[Prefer not to answer])

Scale Summary		
Code	Label	Show-If
1	Yes	
2	No	
99	Prefer not to answer	

63. During the last months, did you have vaginal or anal sex within 2 hours of you using marijuana?

- Yes
- No
- Prefer not to answer

Page Break

---

**Question:** CRCO

**Required**

Scale Summary		
Code	Label	Show-If
1	Never	
2	Once per week or less	
3	2-3 times a week	
4	4-6 times a week	
5	Every day	
99	Prefer not to answer	

64. During the last months, how often did you use crack cocaine?

- Never
- Once per week or less
- 2-3 times a week
- 4-6 times a week
- Every day
- Prefer not to answer

Page Break

---

**Question:** CRCOS2HR  
**Required**  
**Show if:** (VAS.TEXT > 0) and (CRCO ≠ 1:[Never]) and (CRCO ≠ 99:[Prefer not to answer])

Scale Summary		
Code	Label	Show-If
1	Yes	
2	No	
99	Prefer not to answer	

 65. During the last months, did you have vaginal or anal sex within 2 hours of you using crack cocaine?

- Yes
- No
- Prefer not to answer

Page Break

---

**Question:** PRCO

**Required**

Scale Summary		
Code	Label	Show-If
1	Never	
2	Once per week or less	
3	2-3 times a week	
4	4-6 times a week	
5	Every day	
99	Prefer not to answer	

66. During the last months, how often did you use powder cocaine?

- Never
- Once per week or less
- 2-3 times a week
- 4-6 times a week
- Every day
- Prefer not to answer

Page Break

---

**Question:** PRCOS2HR  
